**Serum Ferritin for monthly visits from Day 1 baseline up to Week 48**

Summary statistics of change from baseline (absolute and difference, and 95% CI) will be presented by visit, treatment and subgroups (i.e. by age group, and status of previous iron chelators) and difference between treatments. Graphical presentation including mean (and SD) change from baseline plots will also be reported for all visits.

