To evaluate the overall safety of deferasirox FCT compared with deferasirox DT	Overall safety, as measured by frequency and severity of adverse events and changes in laboratory values of interest during deferasirox FCT (Week 25 to 48) compared with deferasirox DT (Baseline day 1 to Week 24)	
To evaluate efficacy of deferasirox (both DT and FCT) in decreasing serum ferritin levels	Absolute and relative change from baseline (Day 1) in serum ferritin on monthly basis	

4 Study design

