7.2 Assessment types

7.2.1 Efficacy assessments

Serum ferritin testing will be performed in both phases every month. The baseline serum ferritin value will be defined during the screening period.

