Summary statistics of number of pills (and percentages) will also be presented overall and by treatment and subgroups. Refer to [Section 10.5.6](#) for further details.

Serum Ferritin for monthly visits from Day 1 baseline up to Week 48

Summary statistics of change from baseline (absolute and difference, and 95% CI) will be presented by treatment and subgroups and difference between treatments. Further details will be mentioned in SAP.

Palatability

Refer to PRO [Section 10.5.6](#) for details.

mSICT

Refer to PRO [Section 10.5.6](#) for details.

GI symptoms

Refer to PRO [Section 10.5.6](#) for details.

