### **Baseline assessment:**

Baseline assessment in general will be defined as the last assessment prior to the start of the study treatment which is the assessment taken at Day 1 of study. A baseline value refers to the last measurement made prior to administration of first dose of study treatment.

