- Classification to compare baseline to the worst on-treatment value. Apart from the above laboratories summaries, summaries of Hepatitis Viral tests will also be performed.

In addition, a summary of serum ferritin will be presented by TDT and NTDT patients, by age group, and ICT-naive vs. ICT patients by visit.

For all lab assessments, the baseline of each period will be considered based on the actual baseline or start of that particular period, as applicable. Also the baseline data for FCT phase will be provided for only the number of patients available in the analysis set at the start of the period.

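### The planned FCT-minus-DT difference in serum ferritin change from Day 1 measures only the change during FCT, so it does not compare the two formulations

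*SAP*

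**What the plan says.** **The planned contrast.** SAP 2.7.2, under the heading "Serum Ferritin for monthly visits from Day 1 baseline up to Week 48", states: "Summary statistics of change from baseline (absolute and difference, and 95% CI) will be presented by visit, treatment and subgroups". The sentence continues with the words that matter here: "i.e. by age group, and status of previous iron chelators) and difference between treatments". Protocol 10.5.2 plans the same: "Summary statistics of change from baseline (absolute and difference, and 95% CI) will be presented by treatment and subgroups and difference between treatments".

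**The baseline.** The documents place it in three ways.
- Day 1: the endpoint in Protocol Table 3-1 and SAP Table 1.2.1 is "Absolute and relative change from baseline (Day 1) in serum ferritin on monthly basis". The general definition in SAP 2.1.1 agrees: "A baseline value refers to the last measurement made prior to administration of first dose of study treatment".
- Screening: Protocol 7.2.1 says "The baseline serum ferritin value will be defined during the screening period".
- Start of period: SAP 2.8.3, which lists ferritin among the laboratory tests, says "the baseline of each period will be considered based on the actual baseline or start of that particular period". It limits this to where it applies.

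**The design.** The study is single-arm with a fixed order: 24 weeks of DT, then 24 weeks of FCT (Protocol 4.1; SAP 2.1.1, Treatment period). Unplanned switches between formulations are allowed in either period (Protocol 4.2).

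**Status.** SAP 2.7.2 rules out formal hypothesis tests for secondary endpoints. SAP 2.7.3 allows last observation carried forward (LOCF) for ferritin and does not say whether a DT value may be carried into FCT visits.

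**The concern.** Ferritin responds cumulatively to chelation. A value taken during FCT, measured against a pre-DT baseline, contains the whole DT-period change as well as the FCT change. Subtracting the DT change from Day 1 therefore does not set one formulation against the other. It leaves what happened after the switch.

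The result would be printed with a 95% confidence interval and labelled a difference between treatments. A reader would naturally take a negative figure as evidence that FCT lowers ferritin more than DT. SAP 2.7.2 does not say that the period-start baseline in the safety section should be used instead. The screening sentence in Protocol 7.2.1 adds a further ambiguity about the starting value.

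**Working it through.** There is no planned figure to reproduce, because the documents state no expected ferritin change. The check is algebra followed by an illustration with assumed values.

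**Inputs.** Y0, Y24 and Y48 are one patient's ferritin at Day 1, Week 24 and Week 48. Ferritin is measured at all these visits and every 4 weeks from Week 4 (Protocol Table 7-1). FCT starts on Week 25 day 1 (Table 7-1, footnote 5), so Week 24 is the last scheduled value before FCT.

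**Which visits are contrasted.** SAP 2.7.2 does not say. At each scheduled core visit all patients without an unplanned switch are on the same formulation. A same-visit difference could therefore come only from unplanned switchers, and any other difference must cross visits. I take period end (Week 48 against Week 24) and, as an alternative, the average of Weeks 28–48 against the average of Weeks 4–24.

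**Period-end algebra.**
- Day 1 baseline: (Y48 − Y0) − (Y24 − Y0) = Y48 − Y24. The DT change (Y24 − Y0) has disappeared.
- Relative change from Day 1: (Y48 − Y24)/Y0, with the same numerator.
- Period baselines: (Y48 − Y24) − (Y24 − Y0), which does set one change against the other.

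**Illustration.** Assume ferritin falls linearly by X = 500 ng/mL over 24 weeks on DT, and linearly by r × 500 over 24 weeks on FCT. The mean DT change over Weeks 4 to 24 is −500 × (4+8+12+16+20+24)/(24 × 6) = −291.7. The mean FCT change is −500 − r × 291.7 from Day 1, or −r × 291.7 from Week 24.

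| FCT effect relative to DT (r) | Day 1 baseline: end / average | Period baselines: end / average |
|---|---|---|
| 1.5 | −750 / −646 | −250 / −146 |
| 1 (equal) | −500 / −500 | 0 / 0 |
| 0.5 | −250 / −354 | +250 / +146 |
| 0 (plateau) | 0 / −208 | +500 / +292 |

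Values are FCT minus DT in ng/mL; negative favours FCT. With equal slopes and a DT fall of 200 or 1000, the Day 1 difference is −200 or −1000, and the period-baseline difference is 0.

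In the r = 0.5 row the Day 1 contrast has the wrong sign. If ferritin rises on FCT, Y48 − Y24 is positive and the period-end contrast favours DT.

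**Unplanned switchers.** Take a patient who moves from DT to FCT at Week 12, with equal linear slopes. The DT change is −(12/24)X = −0.5X. The change on FCT from its first dose to Week 48 is −(36/24)X = −1.5X. The difference is −X, produced only by unequal durations. A period baseline therefore does not repair the contrast for these patients.

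**Screening against Day 1.** Screening may be up to 28 days before Day 1 (Table 7-1), and pre-treated patients stop their chelator at least 5 days before Day 1 (Protocol 5.2). The two values need not agree.

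**The case against.** **Comparing formulations is not the ferritin objective.** The compliance, satisfaction and safety objectives are worded as FCT against DT. The ferritin objective is the efficacy of both formulations in lowering ferritin, and Day 1 is the right baseline for it. This stands, and it limits the point to one descriptive contrast. A reader might infer that the whole ferritin analysis is invalid; the documents do not support that. It does not remove the point, because both documents still plan the contrast.

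**The SAP already has the remedy.** SAP 2.8.3 sets a period-start baseline for all laboratory assessments, directly after a ferritin summary. This stands in part. The rule sits in the safety section and is conditional, and SAP 2.7.2 still names Day 1. The SAP's change log ties the laboratory baseline definition to Section 2.8.3 and does not list 2.7.2.

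**Three baselines overstates the conflict.** Day 1 is used consistently for the ferritin endpoint and its analysis. The screening sentence is a single outlier in an assessment section, and the period-start rule may serve separate by-period tables. This largely stands. A reader might infer that the report is bound to show contradictory ferritin changes. The conditional wording does not establish that, and cumulative and within-period changes in separately labelled tables would not be an error.

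**The size depends on a steady fall.** Protocol 6.2.1.3 provides for dose reduction at the ferritin target and for considering interruption below it, so a linear 48-week decline is not given. This stands. A reader might infer that FCT must look better even if the formulations are identical; that holds only if ferritin keeps falling on FCT. Nor do period baselines return zero for identical formulations unless the decline is linear: with a plateau by Week 24 they give +X against FCT.

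**Conclusion.** The point holds for the FCT-minus-DT ferritin difference and for nothing wider. Taken from Day 1, the period-end contrast is the change during FCT alone. That is an identity and rests on no assumption about the shape of the decline. The direction depends on ferritin: it favours FCT on a continued fall, is zero on a plateau, and favours DT on a rise. With equal linear slopes the whole of one 24-week DT effect appears as an apparent advantage for FCT: −200, −500 or −1000 ng/mL for assumed DT falls of those sizes.

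The contrast is secondary and untested, so the consequence is a misleading estimate and interval. The primary preference analysis is unaffected. A reader might also infer that period-specific baselines give a fair comparison of formulations. They remove only the arithmetic carry-forward. Formulation remains confounded with period, dose adjustment and a different starting ferritin.

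**What to change.** 1. In SAP 2.7.2, keep change from Day 1 (last value before the first dose) for the overall 48-week course, which is the stated objective.
2. Either drop the FCT-minus-DT difference, or define it as a within-patient difference of within-period changes: from Day 1 for DT, and from the last value before the first FCT dose for FCT. Restrict it to patients without an unplanned switch, and do not carry a value forward across the DT/FCT boundary.
3. If the difference is kept, label it descriptive and state that formulation is confounded with period, dose adjustment and starting ferritin.
4. State in SAP 2.7.2 which baseline governs each ferritin table, so that its relation to SAP 2.8.3 is explicit.
5. Align Protocol 7.2.1 to the Day 1 baseline.

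The cost is wording, one derived variable from ferritin values already collected, and a little more analysis work. The downside is that the retained contrast leaves out unplanned switchers.

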**Palatability**

Refer to PRO section ([Section 2.11](#)) for summary details.

**mSICT**

Refer to PRO section ([Section 2.11](#)) for summary details.

## GI symptoms

Refer to PRO section ([Section 2.11](#)) for summary details.

### 2.7.3 Handling of missing values/censoring/discontinuations

There will be no imputation for missing data. Wherever appropriate, available data will be summarized over specified intervals using suitable summary statistics.

Last observation carried forward can only be applied for serum ferritin levels.

## 2.8 Safety analyses

For all safety analyses, the Safety Set (SAF) will be used. All listings and summaries will be presented by treatment group (wherever applicable) and by TDT and NTDT. In addition, all key safety summaries will be reported separately for all age groups (defined earlier in [Section 2.2.1](#)). The safety analysis will also be presented separately for core and extension phases of the study.

The overall observation period will be divided into three mutually exclusive segments:

1. Pre-treatment period: from day of patient's informed consent to the day before first dose of study medication.
2. On-treatment period: from day of first dose of study medication to 30 days after last dose of study medication.
3. Post-treatment period: starting at day 30+1 after last dose of study medication.

All serious adverse events (SAEs), non-serious adverse events (AEs) and adverse events of special interest (AESI) which are specific gastrointestinal events during the on-treatment period will be summarized.

All data, regardless of observation period, will be listed. Safety assessments starting during the pre-treatment or post-treatment period will be flagged in the listings. Safety assessments starting prior to study day 1 will appear with negative study day in the listings.

### 2.8.1 Adverse events (AEs)

Summary tables for AEs will include only AEs that started or worsened during the on-treatment period, the *treatment-emergent* AEs.

The incidence of treatment-emergent AEs (new or worsening from baseline) will be summarized by system organ class and or preferred term, severity (mild, moderate, severe), type of adverse event, relation to study treatment. If a patient reported more than one AE with the same preferred term, the AE with the greatest severity will be presented. If a patient reported more than one AE within the same primary system organ class, the patient will be counted only once with the greatest severity at the system organ class level, where applicable.

Severity is captured in CRF as per CTCAE V 4.03 grades. The mapping from CTCAE to severity grade is given below:

- Grade 1=Mild
- Grade 2= Moderate

- Grade 3= Severe
- Grade 4 = Life- threatening
- Grade 5= Death related to AE

In this study the grade  $\geq 3$  will be considered as severe.

As appropriate, the incidence of AEs will be presented per 100 patient years of exposure.

The following adverse event summaries will be produced by treatment for Safety Set:

- Adverse events (overall and severe), regardless of study drug relationship by primary system organ class and preferred term
- Adverse events, regardless of study drug relationship by primary system organ class and preferred term and severity
- Adverse events (overall and severe), with suspected study drug relationship by primary system organ class and by preferred term
- Serious adverse events (overall and severe), regardless of study drug relationship, by primary system organ class and preferred term
- Adverse events leading to study drug discontinuation (overall and severe), regardless of study drug relationship, by primary system organ class and preferred term
- Adverse events requiring dose adjustment or study-drug interruption (overall and severe), regardless of study drug relationship, by primary system organ class and preferred term
- Adverse events requiring additional therapy (overall and severe), regardless of study drug relationship, by primary system organ class and preferred term

The incidences listed above will additionally be summarized by preferred term.

- Deaths by primary system organ class and preferred term.
- Non-serious adverse events, regardless of study drug relationship, by primary system organ class and preferred term (for clinicaltrials.gov purpose)

An overall summary of type of AEs (e.g. serious, leading to study drug discontinuation, requiring dose adjustment and/or interruption) will be presented by treatment (overall and severe). This summary as well as the incidence of AEs (overall and severe), regardless of study drug relationship, will additionally be provided separately for pediatric and adult patients. AEs will be summarized by presenting the number and percentage of patients having at least one AE, and having at least one AE by system organ class and/or preferred term, severity, and relation to study drug by treatment. A patient with multiple occurrences of an AE will be counted only once in the AE category.

All AEs, deaths and SAEs (including those from the pre and post-treatment periods) will be summarized and listed and those collected during the pre-treatment and post-treatment period will be flagged. Severity of AEs will be assessed as mild, moderate, or severe.

Separate summaries will be provided for deaths, SAEs, other significant AEs leading to discontinuation, and AEs leading to dose adjustment (including study treatment discontinuation).

A graphical display of relative frequencies within system organ classes and risks difference = risk in FCT-risk in DT (because if in DT, patient count for some SOC becomes 0, then relative risk will be undefined), as appropriate, may be presented by forest plot.

The following formula will be used:

**Table 2-1 Contingency Table for Risk\***

|                          | Treatment |        |
|--------------------------|-----------|--------|
|                          | DFX FCT   | DFX DT |
| No of patient with AE    | FCTE      | DTE    |
| No of Patient without AE | FCTN      | DTN    |

\*separate calculation will be done for each SOC

$$\text{Risk difference (RD)} = \frac{FCTE}{FCTE+FCTN} - \frac{DTE}{DTE+DTN} = p_1 - p_2,$$

$$\text{where } p_1 = \frac{FCTE}{FCTE+FCTN} \text{ and } p_2 = \frac{DTE}{DTE+DTN}$$

The sampling distribution of RD is approximately normal.

$$\begin{aligned} \text{Hence, Standard Error for RD} = \text{SE( RD)} &= \sqrt{\frac{FCTE \cdot FCTN}{(FCTE+FCTN)^3} + \frac{DTE \cdot DTN}{(DTE+DTN)^3}} \\ &= \sqrt{\frac{p_1(1-p_1)}{N_1} + \frac{p_2(1-p_2)}{N_2}}, \end{aligned}$$

$$\text{where } N_1 = FCTE + FCTN \text{ and } N_2 = DTE + DTN$$

$$95\% \text{ CI of SE(RD)} = RD \pm 1.96 \times SE(RD)$$

In plot all results will be presented in percentages (%).

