### 3 Sample size calculation

Based on data from the ECLIPSE study (Taher et al 2018), the following assumptions have been made at Week 48, the patient preference for deferasirox FCT (formulation) is 45% and preference for deferasirox DT (formulation) is 25% and no preference to either of the formulations is 30%. This means the discordant pairs is 70 % (i.e. 70% preferred one formulation over another, 45 %) and concordant pairs= 30% (assuming same preference for each formulation, 15%).

At least 130 patients are needed at Week 48 to have 80% power to detect the difference of patient preference of 20% (i.e. 45% preference of FCT over DT and 25% preference of DT over FCT) at a two sided significance level of 0.05 using McNemar's test for matched pairs.

To allow for roughly 10% of subjects with missing measurement, a total of approximately 145 evaluable patients aged  $\geq 2$  years male or female with TDT or NTDT requiring chelation therapy due to iron overload, need to be enrolled. Patients may have been previously treated with iron chelators (other than deferasirox DT) or be chelation-naïve.

EAST 6.0 is used to calculate the sample size.

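### The optional AE risk-difference plot is meant to cope with zero counts, but its Wald interval ignores the uncertainty of a formulation with no events

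*SAP*

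**What the plan says.** SAP 2.8.1 replaces the relative risk by the risk difference (risk on FCT minus risk on DT). The reason given is "because if in DT, patient count for some SOC becomes 0, then relative risk will be undefined". The display is permissive: "as appropriate, may be presented by forest plot". The footnote to Table 2-1 says "separate calculation will be done for each SOC".

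Below the table the SAP states "The sampling distribution of RD is approximately normal". It gives SE(RD) as the square root of p1(1−p1)/N1 + p2(1−p2)/N2, and the interval as RD ± 1.96 × SE(RD). The interval is labelled as the 95% CI of SE(RD), although it is an interval for RD. There is no minimum count, continuity adjustment, or score or exact alternative.

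The example forest-plot code in SAP 5.4.2 assigns a−b+factor to lcl and a−b−factor to ucl.

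The safety summaries use the Safety Set. By design (SAP 1.1 and the treatment period definition in 2.1.1) the same patients take DT for 24 weeks and then FCT for 24 weeks.

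**The concern.** The risk difference was chosen so that a row with no DT events can still be drawn. That is also where the normal approximation behind the interval is weakest. The point estimate survives a zero count, but its error bar does not: the formulation without events contributes nothing to the standard error, as if its true risk were known to be zero.

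Comparing the safety of FCT and DT is a secondary objective, and this is the only between-formulation AE interval that SAP 2.8.1 specifies. At stake is whether its sparse rows show honest uncertainty. No decision rule or hypothesis test depends on it.

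**Working it through.** **Inputs.** The interval formula is from SAP 2.8.1. SAP section 3 plans for "a total of approximately 145 evaluable patients" and requires at least 130 at Week 48. Those figures reproduce: (1.96 + 0.8416)² × (0.70 − 0.20²)/0.20² = 7.849 × 16.5 = 129.5, so 130; and 130/0.90 = 144.4, so 145. I take 145 patients on DT and assume 135 on FCT, between 130 and 145. The documents give no expected SOC incidence, so the event rates below are assumptions, shown as ranges.

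**Step 1: the zero count.** With no DT events p2 = 0, so p2(1−p2)/N2 = 0 and only FCT uncertainty remains. The exact 95% upper limit for 0/145 is 1 − 0.025^(1/145) = 2.5%. With zero on both, SE = 0 and the interval is 0 to 0. Zero DT counts are plausible only for rare SOCs: P(no DT events) = (1−p)^145, which is 48% at p = 0.5%, 23% at 1% and 5% at 2%.

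**Step 2: intervals at 135/145.** Worked case, 4 v 0: p1 = 4/135 = 2.963%; SE = √(0.02963 × 0.97037/135) = 1.459%; 2.963 ± 1.96 × 1.459 gives 0.10 to 5.82 points. Newcombe's independent-sample interval combines Wilson limits, 1.158% to 7.371% for 4/135 and 0 to 2.581% for 0/145. Its lower limit is 2.963 − √((2.963−1.158)² + 2.581²) = −0.19 and its upper limit is 7.37.

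| Events, FCT v DT | SAP Wald (points) | Newcombe (points) |
|---|---|---|
| 0 v 0 | 0.00 to 0.00 | −2.58 to 2.77 |
| 1 v 0 | −0.71 to 2.19 | −1.91 to 4.08 |
| 2 v 0 | −0.56 to 3.52 | −1.31 to 5.24 |
| 3 v 0 | −0.26 to 4.71 | −0.74 to 6.33 |
| 4 v 0 | 0.10 to 5.82 | −0.19 to 7.37 |
| 0 v 3 | −4.39 to 0.25 | −5.91 to 1.02 |

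**Step 3: coverage of the SAP interval.** Exact enumeration of two independent binomials at 135/145:

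| True rates, FCT v DT | Coverage |
|---|---|
| 1% v 0.5% | 86.0% |
| 0.5% v 1% | 87.2% |
| 2% v 1% | 92.5% |
| 1% v 2% | 93.1% |
| 3% v 1% | 94.4% |
| 5% v 3% | 95.0% |
| 0.5% v 0.5% | 99.4% |
| 1% v 1% | 97.3% |
| 2% v 2% | 94.7% |
| 3% v 3% | 94.7% |
| 5% v 5% | 95.0% |

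For FCT 1% v DT 0.5%, coverage is 87.7% at 145/145 and 85.4% at 130/145, so the choice of 135 matters little. With DT at 0.2% to 1% and FCT higher (up to 15%), coverage runs from 63.6% to 94.5% at 145/145 and from 60.8% to 94.6% at 130/145.

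**Step 4: pairing.** Independence was assumed only to isolate the zero-count effect. In a paired simulation (145 patients, 200,000 runs), coverage of the SAP interval at within-patient correlation 0, 0.2 and 0.4 was:

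- FCT 3%, DT 1%: 93.0%, 94.3%, 95.7%.
- FCT 2%, DT 0.5%: 93.6%, 94.1%, 94.5%.
- 30% on both: 94.8%, 97.0%, 98.8%.

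Adding only a covariance term does not repair zero cells. If all n patients are seen on both formulations, b have events on FCT only and none on DT, the paired Wald variance is (b − b²/n)/n² = p1(1−p1)/n, the same as the SAP's. Simulated paired Wald coverage was 90% to 94% for the two rare-event cases.

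**Step 5: the code.** The reversed lcl and ucl do not move the plotted point, which is their midpoint, and the bar spans the same two values. The PROC PRINT step would list the limits under the wrong names.

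**The case against.** The case for leaving the formula alone has real force.

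- A reader might infer that the plot could show a clear difference on one to three events. It cannot against a zero count: every such interval in the table includes 0, and exclusion begins at four events.
- A reader might infer that the interval generally covers less than 95%. It does not. With equal rare rates it over-covers, and at equal rates of 2% to 5% coverage is 94.7% to 95.0%, so spurious exclusion of 0 is not materially inflated. Positive within-patient correlation removes much of the shortfall where rates differ.
- A reader might infer that the plan predicts zeros. Its wording is conditional, and a whole SOC pools many terms.
- A row with no events on either formulation may never be drawn: the example graph is titled for the most frequent events, and the documents do not say empty SOCs will be shown.
- The plot is optional, and counts and percentages by SOC are tabulated anyway, so a zero is visible.

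All of this stands and limits the importance of the point. It does not rescue the formula in the case that motivated the risk difference: at a zero count one formulation's uncertainty is omitted. At 4 v 0 that decides whether the bar crosses the zero line.

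**Conclusion.** The interval is wrong as written for sparse rows, with minor consequences. That the variance term vanishes at a zero count needs no assumption. The size of the effect does: under independence at 135/145, coverage is about 86–87% for 1% v 0.5% and about 93% for 2% v 1%, but 97% and 99% when both rates are 1% and 0.5%. The event rates, the FCT denominator and the within-patient correlations are assumed, and the documents support no single value.

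The formula also treats DT and FCT as separate samples, although the same patients take both. With positive correlation this pushes the other way, towards intervals that are too wide, most clearly for common events.

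Nothing here touches the primary preference analysis, and the documents do not support reading it as a threat to the overall safety conclusions. The lcl/ucl reversal is a real slip, confined to printed labels in example code.

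**What to change.** In SAP 2.8.1:

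- Replace the formula under Table 2-1 with a score-based interval for the paired risk difference (Tango's, or Newcombe's paired form), applied to patients observed on both formulations. This handles zero cells and respects the design. The independent-sample Newcombe figures above illustrate the zero-count effect only; the paired score interval was not computed here.
- Remove the unconditional normality statement and label the interval as the CI of RD.
- State whether SOCs with no events on either formulation are plotted.

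In SAP 5.4.2, swap the lcl and ucl assignments and replace the Wald calculation to match.

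The cost is a few lines of SAP text and code, plus a paired event indicator per patient and SOC in place of two marginal counts. Intervals for rare events become somewhat wider and conservative: in its independent form Newcombe covers about 99.7% at 1% v 0.5%. Patients seen on only one formulation drop out of the interval, though they remain in the tabulated Safety Set counts, so the plot needs a footnote giving its denominator.
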